7.3.2.9. Medical assessment of physical symptoms

The following diseases or syndromes will be confirmed for the presence or absence, time of onset/disappearance, relationship with ATTR, severity^{*}, etc.

[Timing of assessment] At the start of treatment (results immediately before treatment) to the end of observation period or at discontinuation of treatment with this drug

*Follow the following classification for the assessment of severity.

1: Mild

The symptom is mild and usually transient. It may require short-term treatment (drug or non-drug therapy) but does not limit the patient's daily activities.

2: Moderate

The symptom is moderate. The symptom may require continuous treatment (drug, special treatment) and limit the patient's daily activities. In most cases, the patient is capable of self-care, but may require occasional assistance or other procedure (hospitalization or medical procedure). 3: Severe

The symptom is severe. Severe symptoms may be transient but are accompanied by marked disability or pain. They require treatment (drug therapy or hospitalization) and special assistance to improve symptoms. Severe symptoms may be progressive and/or life-threatening and require further treatment to maintain the patient's condition, although improvement of symptoms cannot be expected.

(1) Neurologic

(2) Eye

(3) Cardiovascular

Follow the follo	owing classification for the severity of heart failure:
[NYHA Grade	New York Heart Association Classification]
Class I:	Subjects with cardiac disease but without resulting limitations of physical activity. Ordinary physical activity does not cause undue fatigue, palpitation, dyspnea, or anginal pain.
Class II:	Subjects with cardiac disease resulting in slight limitation of physical activity. They are comfortable at rest.
	Ordinary physical activity results in fatigue, palpitation, dyspnea, or angina pain.
Class III:	Subjects with cardiac disease resulting in marked limitation of physical activity. They are comfortable at rest.
	Less than ordinary physical activity causes fatigue, palpitation, dyspnea, or anginal pain.
Class IV:	Subjects with cardiac disease resulting in inability to carry on any physical activity without discomfort.
	Symptoms of cardiac insufficiency or of the anginal syndrome may be present even at rest. If any physical activity is undertaken, discomfort is increased.

- (4) Genitourinary/Renal/Reproductive
- (5) Gastrointestinal

(6) Endocrine/Metabolic

(7) Musculoskeletal

(8) Respiratory

(9) Psychiatric

7.3.2.10. End-of-study (discontinuation) record

Confirm whether or not treatment can be continued by this drug during the observation period. If treatment with this drug cannot be continued or if the study is discontinued because the dose of this drug was changed for the treatment of ATTR-CM, enter the date of the last visit (date of the last dose of 20 mg if the dose of this drug was changed for the treatment of ATTR-CM) and reason for discontinuation. If an adverse event was selected as the reason for discontinuation, enter the detailed information in the adverse event column.

- (1) Date of the last visit (date of the first visit after the last dose of this drug)
- (2) Reason for discontinuation

7.3.2.11. Effectiveness evaluation

The following 10 items should be evaluated for effectiveness:

(1) NIS (See Section 7.3.2.8.5.)

Evaluate the NIS total score, the NIS Upper Limb (NIS-UL) total score, the NIS Lower Limb (NIS-LL) total score, scores of cranial nervous system (sum of items 1 to 5), muscle weakness (sum of items 6 to 24), tendon reflex (sum of items 25 to 29), and sensation (index finger: sum of items 30 to 33, great toe: sum of items 34 to 37).

(2) Norfolk QOL-DN (See Section 7.3.2.8.6.)

Evaluate the TQOL scores (sum of all 35 items) and 5 domain scores (physical function/large nerve fiber disorder score, activities of daily living score, symptom score, small nerve fiber disorder score, and autonomic neuropathy score).

(3) Modified Body Mass Index (mBMI)

mBMI is calculated by multiplying BMI by serum albumin level.

(4) Ambulatory status (ambulatory ability scale in polyneuropathy dysfunction score)

Evaluate the ambulatory status (see Section 7.3.2.8.7 for details).

(5) Motor

Evaluate the motor function with MRC (16 items in total) (see Section 7.3.2.8.8 for details) scale. (6) Reflexes

Evaluate the tendon reflexes (5 items in total) (see Section 7.3.2.8.8 for details).

(7) Light Touch

Evaluate the tactile (11 items in total) (see Section 7.3.2.8.8 for details).

(8) Pin Prick

Evaluate the pain sensation (11 items in total) (see Section 7.3.2.8.8 for details). (9) Vibration

Evaluate the vibration sense (6 items in total) (see Section 7.3.2.8.8 for details). (10) Position Sense

Evaluate the positional sense (4 items in total) (see Section 7.3.2.8.8 for details).

7.3.2.12. Adverse events

Occurrence of adverse events (AEs) from the start date of administration of this drug to the end date of observation period should be confirmed and the following information should be recorded. If any AE is

observed, the investigator will take appropriate measures, promptly report it to Pfizer, and in principle, transcribe and confirm the course until the symptom disappears.

Also, further investigation should be separately conducted, if deemed necessary by Sponsor for patients who experienced a serious adverse reaction, an unexpected adverse reaction or other adverse reactions not listed in the package insert.

- (1) Presence/absence of AE
- (2) Name of AE
- (3) Date of occurrence
- (4) Intervention
- (5) Seriousness
- (6) Outcome
- (7) Causal relationship to this drug

If the AE is associated with abnormal laboratory values, i.e., clinical laboratory tests, the following information should also be recorded:

- (1) Laboratory parameter
- (2) Site reference value
- (3) Unit
- (4) Date measured
- (5) Results

Note: AEs are any and all unfavorable events (including clinically significant abnormal changes in laboratory tests) occurring in patients after starting the targeted drug treatment regardless of their causal relationship. Serious adverse events (SAEs) are any unfavorable medical occurrences that result in death, are life-threatening, require (or prolong) hospitalization, cause persistent or significant disability/incapacity, result in congenital anomalies or birth defects, or are other conditions which represent significant health hazards.

7.3.2.13. Confirmation of survival

For patients who completed the study, the following information will be entered 3 years after the start of treatment with this drug at the own site for confirmation of survival:

- (1) In the case of survival: Date of survival confirmed
- (2) In the case of death: Date of death, cause of death (TTR-FAP/other than TTR-FAP) (If the date of death is unknown, the last date of survival confirmed and the date of information on death obtained)

Among the patients who discontinued the study, their survival will be confirmed using the attached CRF 3 years after the start of treatment for patients who discontinued the study because the reason for discontinuation as follow-up after discontinuation of treatment is other than transfer to another hospital/department, no return to the hospital, or having adverse events resulting in death as outcome and for patients who discontinued the study for the treatment of ATTR-CM.

- (1) In the case of survival: Date of survival confirmed
- (2) In the case of death: Date of death, cause of death (TTR-FAP/other than TTR-FAP)

(If the date of death is unknown, the last date of survival confirmed and the date of information on death obtained)

(3) If survival or death is unknown: Last date of survival confirmed

For patients who started the treatment with this drug after May 2018 (1.5-year observation period), their survival should be confirmed using the attached CRF 1.5 years after the start of treatment at the own site.

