Survival time will be evaluated by setting death as the event of interest. For patients who complete the study, survival status will be determined on the first follow-up date exceeding 3 years after the start of treatment with this drug at the own site. In the case of death, information on the cause, i.e., whether the death is due to TTR-FAP or to another cause (including unknown) will also be collected. *For patients who started the treatment with this drug after May 2018 (1.5-year observation period), their survival should be confirmed using the attached CRF* on the first follow-up date exceeding *1.5 years after the start of treatment at the own site.* 

The following two kinds of event will be evaluated:

- Death from any cause
- FAP-related death (Death from TTR-FAP is set as the event of interest. Death with missing cause will
  not be regarded as an event of interest.)

Time to event will be evaluated with respect to the following two kinds of time:

- Time from start of treatment to event
- Time from onset of FAP to event

CC				
I				
l				

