#### 7. HANDLING OF MISSING DATA

Adverse Events

If the severity of, action taken for, or outcome of an AE is missing, their value will be considered "unknown" for data summarizations.

– NIS

If the evaluation result for the right or left side on the same day is missing, the value for the evaluated side will be adopted as the score for the item.

– QOL-DN

If the score of an item included in the Physical Function/Large Nerve Fiber Disorder subscale, Activities of Daily Living subscale, Symptoms subscale, Small Nerve Fiber Disorder subscale, or Autonomic Neuropathy subscale is missing, the missing score will be imputed with the mean score from the evaluated items in the relevant subscale as long as  $\geq 60\%$  of the items in the subscale have been evaluated. The score for the subscale will be determined by summing the scores for the evaluated and imputed items.

The TQOL score will be determined by summing the scores for the evaluated and imputed items if all the 35 items have been evaluated or all missing values imputed by using the aforementioned method. If imputation could not be done by the aforementioned method for some items because of failure of evaluation for  $\geq 60\%$  of all items in a subscale, the TQOL score will be determined as 35 times the mean from the evaluated and imputed items, provided that at least 60% of all items have been evaluated or imputed. If  $\geq 40\%$  of the items in a subscale or the TQOL score are missing, the score for the subscale and the TQOL score will be treated as missing values.

Neurological Assessment

If the item toe extension and/or toe flexion in the motor domain have been evaluated and the results are directed to normal, other items in the same domain will be imputed with those directed to normal. If the item triceps surae in the reflexes domain has been evaluated and the result is normal, other items in the same domain will be imputed with normal. If the item toe in the light touch, pin prick, vibration, or position sense domain has been evaluated and the result is normal, other items in the same domain will be imputed with normal.

- Evaluation of Survival Time

If the cause of death is missing in the record of a death-confirmed patient, the patient will be treated as having died for unknown cause.

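### For patients stopped by a fatal adverse event, no visible item captures date of death or TTR-FAP cause, so the missing-cause rule may bias FAP-specific survival upward

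*Protocol*

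**What the plan says.** Protocol 7.3.2.13 sets out the survival items, including "In the case of death: Date of death, cause of death (TTR-FAP/other than TTR-FAP". They apply to patients who complete the study. Among patients who discontinue, they apply at 3 years to those who left for treatment of ATTR-CM and to those whose reason "is other than transfer to another hospital/department, no return to the hospital, or having adverse events resulting in death as outcome". For patients who started after May 2018, "their survival should be confirmed using the attached CRF 1.5 years after the start of treatment at the own site", and no exclusion for fatal adverse events is written there.

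A patient who dies of an adverse event on treatment is recorded in two other places. The discontinuation record (Protocol 7.3.2.10) takes the last visit date and the reason, and adds: "If an adverse event was selected as the reason for discontinuation, enter the detailed information in the adverse event column". The adverse event items (Protocol 7.3.2.12) are presence, name, date of occurrence, intervention, seriousness, outcome and "Causal relationship to this drug".

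SAP 6.2 states that, for deaths, "whether the death is due to TTR-FAP or to another cause (including unknown) will also be collected". It defines FAP-related death as one of two events and says a death with missing cause will "not be regarded as an event of interest". SAP 7 adds: "If the cause of death is missing in the record of a death-confirmed patient, the patient will be treated as having died for unknown cause". SAP 8.2.4.6 right-censors other deaths when FAP-related death is the event.

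**The concern.** Deaths during treatment are central to a survival analysis that starts at first dose. The protocol directs exactly these patients away from the form that asks for date of death and for TTR-FAP or other cause. The SAP then resolves a missing cause in one direction only, as not FAP-related.

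If the cause is in fact missing for some of these deaths, FAP-specific survival will look better than it is. This touches two of the four planned survival analyses (FAP-related death, timed from start of treatment and from FAP onset). The study has no control group (Protocol 7.9), so these estimates stand alone, and the final analysis supports reexamination (SAP 3). The date of death has the same gap, and the all-cause analysis also needs it.

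**Working it through.** **1. Where the two items are listed, for a patient with 3-year follow-up who stops because of a fatal adverse event**

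| Record | Used for this patient? | Date of death | TTR-FAP/other cause |
|---|---|---|---|
| Protocol 7.3.2.13, completers | No, not a completer | Listed | Listed |
| Protocol 7.3.2.13, discontinued patients | No, left out by its terms | Listed | Listed |
| Protocol 7.3.2.10, discontinuation record | Yes | Not listed | Not listed |
| Protocol 7.3.2.12, adverse event items | Yes | Not listed | Not listed (asks relation to the drug) |
| Protocol 9 and 9.1, SAE report form | Yes | Form items not shown | Form items not shown |
| SAP 8.2.3.2, list of deaths | Yes | Not listed (event onset date) | Not listed (relation to the drug) |

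**2. What the SAP does with a missing cause**

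Missing becomes unknown (SAP 7). Unknown is grouped with causes other than TTR-FAP and is not an event of interest (SAP 6.2). Deaths that are not events are right-censored (SAP 8.2.4.6).

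**3. Direction**

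A FAP death with a missing cause leaves the risk set at the same time either way, but no event is counted. The estimated FAP-specific hazard falls and the survival curve rises. It cannot move the other way.

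**4. Size**

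The plan gives no expected deaths, FAP mortality or survival rate, so there is no figure of its own to reproduce for the bias. Its only sizing figure does reproduce: 0.87 × 127.54 = 110.96 and 1.1 × 127.54 = 140.29, matching approximately 111 to 140 patients (Protocol 7.5.2). It is used below only for scale.

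Inputs, all assumed: S, the true 3-year FAP-specific survival, and q, the share of all FAP deaths left without a cause, with a constant FAP-specific hazard and q constant over follow-up. The hazard estimated is then (1 − q) times the true one, so reported survival tends to S^(1 − q).

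| True S | q = 0 | q = 0.25 | q = 0.5 | q = 1 |
|---|---|---|---|---|
| 95% | 95.0% | 96.2% | 97.5% | 100% |
| 90% | 90.0% | 92.4% | 94.9% | 100% |
| 80% | 80.0% | 84.6% | 89.4% | 100% |

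For example, 0.80^0.75 = 0.846 and 0.80^0.5 = 0.894, overstatements of 4.6 and 9.4 points.

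In counts, if all patients were followed for 3 years, 20% FAP mortality would mean 0.20 × 111 = 22.2 to 0.20 × 140 = 28.0 FAP deaths. With q = 0.5, the cause would be missing for 11.1 to 14.0 of them.

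**The case against.** The case against is substantial.

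- **The exclusion has an ordinary reading.** The form asks, 3 years on, whether a discontinued patient is alive, and a patient already known to have died need not be asked. That explains vital status. It does not supply the date and cause that the same items collect.
- **Cause may come from elsewhere.** Progression of the underlying disease counts as an adverse event (Protocol 9.4.1), so the event name can identify a TTR-FAP death. Every SAE goes on a report form handled as part of the CRF (Protocol 9 and 9.1), with more detail than the CRF and any autopsy summary. This stands as a possible source. It is not a stated one: a fatal cardiac or infectious term would not settle the question, and no visible passage maps event terms or SAE narratives to TTR-FAP or other.
- **SAP 6.2 says cause will be collected, without exception.** It does, but the protocol lists no item for doing so in these patients.
- **The case-handling outline in SAP 8.2.4.6 is a figure not shown in the text reviewed.** It may contain the mapping, so its absence cannot be claimed. If it does, what remains is whether the inputs it needs were collected.
- **Scope is limited.** No such exclusion is written for patients who started after May 2018.
- **The stakes are limited.** No hypothesis is tested (SAP 4), and death from any cause is analysed alongside and does not depend on the cause item.

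A reader might infer that these deaths cannot count as FAP-related and that FAP-specific survival is therefore overstated. The documents do not support that. Having no dedicated item is not the same as having no recorded cause, and the missing-cause rule applies only where the cause is in fact missing.

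**Conclusion.** The point holds as a gap in the visible plan, limited to patients with 3-year follow-up who discontinue because of a fatal adverse event. For them no visible item captures date of death or TTR-FAP/other cause, and no visible rule says where the two come from. Their deaths may therefore fall under the missing-cause rule, be censored, and bias FAP-specific survival upward.

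The direction is certain for any FAP death whose cause is missing. The size is not known. It is nil if the cause is recovered for every death; the other values shown rest entirely on assumed S and q.

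This is a cheap improvement rather than a must-fix, given that the analysis is descriptive and all-cause survival is also reported.

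**What to change.** 1. In Protocol 7.3.2.13, require date of death and TTR-FAP/other cause for every death, including patients whose reason for discontinuation is an adverse event with fatal outcome.
2. For data already collected, obtain both items before database lock through the query route in Protocol 7.6.5.2, or take them from the SAE report under a mapping stated in the SAP. This is the operative step if collection has closed: its planned end was May 2021, and SAP version 10.0 is dated March 2023.
3. In SAP 6.2 and 7, apply the missing-cause rule only to deaths still unclassified after step 2, and report their number.
4. Add a sensitivity analysis counting those remaining deaths as FAP-related. With the planned analysis it brackets the effect of the missing causes.

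The cost is one query for each fatal adverse event, a sentence or two in each document, and one extra run of an analysis already planned.

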5. RATIONALE AND BACKGROUND

Transthyretin familial amyloid polyneuropathy (TTR-FAP) is a rare, highly heritable disease in which amyloid derived from transthyretin (TTR) is deposited in the peripheral and autonomic nervous systems, thereby causing dysfunction. In Japan, patients are accumulated in Nagano and Kumamoto prefectures. It is known that the onset of the disease in the accumulated area is young in the 30s and the duration of survival after the onset is approximately 10 years, which is extremely poor prognosis. However, the only treatment for TTR-FAP in Japan has been symptomatic treatment for each of the various symptoms associated with the disease. Liver transplant has been performed as the only method to suppress the

> Pfizer Confidential Page 10 of 37

disease progression, but the target patients for liver transplant are very limited due to problems such as lack of donors and risk of transplant surgery.

Vyndaqel (generic name: tafamidis meglumine) is a therapeutic agent for TTR-FAP with a novel mechanism of action that suppresses amyloid formation by binding to the thyroxine (T4) binding site of the TTR tetramer, stabilizing the TTR tetramer, and inhibiting its dissociation into monomers. The overseas clinical studies started in 2007 demonstrated the efficacy of Vyndaqel not only in delaying the progression of peripheral neuropathy, suppressing the decline of quality of life (QOL) and improving nutritional condition in patients with TTR-FAP but also in stabilizing TTR early after the start of treatment and maintaining TTR stabilization throughout the study period. As a result, Vyndaqel was approved in Europe in November 2011 and has been in the market. In Japan, the phase 1 study confirmed no difference in pharmacokinetics, TTR stabilization, and safety between Japanese and non-Japanese subjects. Furthermore, the domestic phase 3 clinical study in Japanese adult patients with TTR-FAP also demonstrated the efficacy and safety of Vyndaqel equivalent to those in the results of the overseas clinical studies. As a result, the application for approval was filed in February 2013 and the drug was approved in September 2013.

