7.7. Data analysis

1. Definition of analysis set

The safety analysis set (SAS) consists of all patients who received this drug at least once. The effectiveness analysis set consists of those for whom the effectiveness evaluation was conducted at least once among the SAS. The details will be described in the separately prescribed Statistical Analysis Plan (SAP).

2. Method of analysis

(1) Major analysis for safety evaluation

The occurrence of ADRs and the incidence of ADRs (percentage of patients with AEs for which the causal relationship with this drug cannot be ruled out) will be calculated in the SAS.

(2) Major analysis for effectiveness evaluation

For NIS, QOL-DN, and mBMI, their values and changes from baseline at each time point will be calculated in the effectiveness evaluation set. For ambulatory status, motor function (MRC), tendon reflex, tactile sense, pain sensation, vibration sense, and positional sense, changes from baseline at each time point will be calculated. In addition, survival time analysis will be performed using survival information obtained up to 3 years after the start of treatment.

Detailed methodology for summary and statistical analyses of data collected in this study will be documented in a SAP, which will be dated, filed and maintained by Pfizer. The SAP may modify the plans outlined in the protocol; any major modifications of primary endpoint definitions or their analyses would be reflected in a protocol amendment.

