#### 8.1.5. Time (to event) data

For time data containing right-censored data, Kaplan-Meier's method will be used to determine the median, 1st quartile, and 3rd quartile. Kaplan-Meier plots will also be presented, as necessary.

For time data containing interval censored data, the EMICM algorithm will be used to determine the median, 1st quartile, and 3rd quartile. Estimated survival plots will also be presented, as necessary. A reference program is shown in Section 10.3.1.

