#### 8.2. Statistical Analyses

#### 8.2.1. Description of patients

#### **Combination clinical practice**

Given the nature of this disease as a rare disease, patients may be treated (or receive prescriptions of this drug) at multiple sites during the observation period (combination clinical practice). For possible patients

PFIZER CONFIDENTIAL Page 23 with combination clinical practice, identification will be determined at a case conference using information on birthdate, sex, mutant genotype, and names of combination practice sites or sites after patient transfer. In principle, data at the site with earlier date of treatment initiation will be adopted for the analysis of patient characteristics. All data after the start of treatment for an identical patient will be combined and handled using this start date of treatment as the origin (data linkage).

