## 8.2.4.6. Evaluation of survival time

Each time to each event  $(2 \times 2)$  noted in the evaluation of survival time in Section 6.2 will be analyzed as described in Section 8.1.5. Survival rates will also be calculated at 1.5 and 3 years for the time from the start of treatment to the event and at 10 and 20 years for the time from FAP onset to the event (enter NA if not estimable). When death related to FAP is an event, other deaths will be right-censored.

[figure not shown]
The outline of how to handle cases at the time of analysis in the evaluation of survival time is shown below.

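### Three-year vital status is not sought after transfer or no return; if those lost die faster than those followed, Kaplan-Meier survival at 3 years will be too high

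*Protocol*

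**What the plan says.** Protocol 7.3.2.13 sets the survival check by group.

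- Completers: vital status at 3 years from the start of treatment at the own site.
- Patients who stopped the study for ATTR-CM treatment: checked at 3 years.
- Other discontinuers: checked at 3 years when the reason is "other than transfer to another hospital/department, no return to the hospital, or having adverse events resulting in death as outcome".
- Patients starting after May 2018: "their survival should be confirmed using the attached CRF 1.5 years after the start of treatment at the own site". This sentence has no exclusion by reason for discontinuation.

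The form for discontinuers already has a field for unknown vital status, to be filled with the last date the patient was known alive.

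Protocol 7.7 states that "survival time analysis will be performed using survival information obtained up to 3 years after the start of treatment". SAP 5.2 lists survival time among the efficacy endpoints. SAP 8.1.5 gives the estimator: "For time data containing right-censored data, Kaplan-Meier's method will be used to determine the median, 1st quartile, and 3rd quartile", with a separate algorithm for interval-censored data. SAP 8.2.4.6 adds: "Survival rates will also be calculated at 1.5 and 3 years for the time from the start of treatment to the event". It then says "The outline of how to handle cases at the time of analysis in the evaluation of survival time is shown below", but that figure is not reproduced in the text available.

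On patients who move, Protocol 7.2.1 takes in every site and department using the drug. SAP 8.2.1 links one patient's records across sites, using among other items the "names of combination practice sites or sites after patient transfer".

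**The concern.** The plan treats survival after stopping the drug as in scope, since most discontinuers are followed to 3 years. The gap falls on two groups defined by how they left. Protocol section 5 says of the accumulated areas that "the duration of survival after the onset is approximately 10 years, which is extremely poor prognosis". In such a disease, patients who stop attending or change hospital are plausibly not a random sample of those at risk.

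Kaplan-Meier estimation assumes that patients censored at a given time have the same later risk as those still followed. If patients lost in these two ways have a higher risk, the 3-year rate is too high, for death from any cause and potentially for FAP-related death. The confidence interval will not show this.

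**Working it through.** **1. The plan's only size figure.** Protocol 7.5.2 multiplies prevalence by population: 0.87 × 127.54 = 110.96 and 1.1 × 127.54 = 140.29. This reproduces its 111 to 140 patients, used below for scale. The documents state no expected survival, loss rate or mortality after loss.

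**2. Who is left without a vital status.**

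- *Fatal adverse event:* nothing is lost, because the death is recorded.
- *Transfer, still on the drug:* the receiving site should register the patient (Protocol 7.2.1, 7.3.1). Completeness is checked yearly during the registration period (7.6.4), and SAP 8.2.1 links the records. These patients are largely recoverable.
- *Transfer, not recovered:* the drug stops on transfer, the move follows the close of registration in November 2019 (7.2.2), or the records are not matched.
- *No return:* no visible recovery route.

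Protocol 7.2.4 uses the last visit for patients lost to follow-up. That points to censoring there, but the SAP's own rule for survival cannot be read.

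**3. Size, under stated assumptions.** Let λ = 0.04 per year be the death hazard while followed, and p the 3-year probability of leaving unrecovered (ignoring death), so that g = −ln(1 − p)/3. Let k be the hazard ratio after leaving. Censoring at departure, Kaplan-Meier tends to exp(−3λ) = exp(−0.12) = 0.8869 whatever k is. True survival is

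S(3) = exp(−3(λ + g)) + ∫₀³ g·exp(−(λ + g)u)·exp(−kλ(3 − u)) du.

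Example, p = 0.15 and k = 3: g = 0.0542; the first term is exp(−0.2825) = 0.7539, the integral is 0.1179, and S(3) = 0.8718. The overestimate is 0.8869 − 0.8718, or 1.5 points.

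True S(3), with the Kaplan-Meier error in points in brackets (taken before rounding):

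| p | k = 0.5 | k = 1 | k = 2 | k = 3 | k = 5 |
|---|---|---|---|---|---|
| 10% | 0.8897 (−0.28) | 0.8869 (0) | 0.8817 (+0.52) | 0.8769 (+1.00) | 0.8684 (+1.85) |
| 15% | 0.8911 (−0.42) | 0.8869 (0) | 0.8790 (+0.79) | 0.8718 (+1.51) | 0.8589 (+2.81) |
| 25% | 0.8940 (−0.71) | 0.8869 (0) | 0.8735 (+1.34) | 0.8612 (+2.57) | 0.8393 (+4.76) |

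**4. Bounds in the same model.** If all those lost die on leaving, S(3) = exp(−3(λ + g)). If all survive to 3 years, S(3) = 1 − [λ/(λ + g)]·[1 − exp(−3(λ + g))]. For p = 15% these give 75.4% and 89.5%; for p = 25%, 66.5% and 90.1%.

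**5. A different starting point.** Take a median survival of 10 years, so λ = ln 2/10 = 0.0693 and exp(−3λ) = 81.2%. This borrows the protocol's figure, which runs from onset and not from start of treatment. With 20% observed to leave before death by 3 years, the overestimate is 1.8, 3.4 and 6.0 points for k = 2, 3 and 5. A simulation of 1,000,000 patients agreed for k = 3 (true survival 0.778 against 0.812). If linkage recovers half of the losses, leaving 10%, the k = 3 figure falls from 3.4 to 1.7.

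Across 3-year survival of 70 to 90%, 5 to 30% lost and k from 2 to 5, the overestimate is 0.2 to 12.2 points. At k = 0.5 it is an underestimate of 0.1 to 2.5.

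**6. Scale.** With complete follow-up and S = 0.887, the 95% half-width is 1.96 × √(0.8869 × 0.1131/n): 5.9 points at n = 111 and 5.2 at n = 140.

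**The case against.** The strongest reply is that the transfer exclusion avoids duplicate follow-up. In an all-patient, all-site study a transferred patient on the drug belongs to the receiving site, which runs its own survival check. That stands for most transfers, so transfer is the weaker part of the point and no return the stronger.

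A reader might infer that survival *is* overestimated. The documents do not support that. The direction needs a higher death hazard after leaving, and they give neither that hazard nor the reasons for leaving. The prognosis in Protocol section 5 describes patients in the accumulated areas generally, not those who leave.

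A reader might also infer that the plan has no sensitivity analysis or that its censoring rule is wrong. The case-handling figure in SAP 8.2.4.6 is not shown and other SAP text is redacted, so one can say only that none is visible. Even so, no handling rule can supply a vital status that was never collected.

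Nor does the text exclude anyone from the 1.5-year check. The written exclusion belongs to the 3-year check.

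Three practical replies carry weight. Data come from the site's own charts (Protocol 7.1, 7.4), so many forms for patients who never returned would read unknown. Data collection was planned to end in May 2021, while SAP version 10.0 is dated March 2023. Survival is descriptive, with no hypothesis or decision rule (SAP 4.1, 4.2), no control group, and hepatotoxicity as the major investigation item. SAP 8.2.1 already tabulates discontinuations by timing and reason, and Protocol 7.9 admits missing data in general terms. Neither carries this loss into the survival estimate.

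**Conclusion.** The point holds in conditional form. The 3-year check leaves vital status unsought for patients who do not return and for transfers that linkage misses, while other discontinuers are followed. This is a written rule that can cause informative censoring of a named endpoint.

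With 3-year survival near 89%, 10 to 25% lost and unrecovered, and a hazard ratio of 2 to 5, the overestimate is about 0.5 to 4.8 points. Every one of these inputs is an assumption. The error shrinks as linkage recovers transfers. It is generally smaller than the sampling half-width of 5 to 6 points but approaches it at the top of the range. It should be addressed, but it does not undermine the study's main safety purpose.

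**What to change.** **Protocol 7.3.2.13.** Remove the exclusions for no return and for transfers not recovered by linkage, including department moves within one hospital, where the chart may hold the answer. The site completes the existing survival form at 3 years from available records, using the unknown field where needed. State that the 1.5-year check likewise applies whatever the reason for discontinuation.

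**SAP 8.2.4.6.** After linkage, report the number censored before 3 years (1.5 years for later starters), separately for transfer and no return. Add two sensitivity analyses, labelled as bounds and not as plausible estimates: these patients counted as dead at the last confirmed date, and as alive to the end of the horizon.

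If data collection has closed, do the SAP part alone; it needs only data already held.

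**Cost.** A short amendment if collection is open, a few extra site queries (many returning unknown), and two extra analysis runs.
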